3.5.3. Stratification

All analyses on AF patients will be stratified on age-group: <80, 80-90, > 90 years old.

All analyses on AF patients exposed and unexposed to OAC, will be stratified on modified CHA₂DS₂VASC score strata (18), low risk (score 0 in males or 1 in females); moderate risk (score 1 in males or 2 in females); high risk if ≥2 for males and ≥3 females.

All analyses where the event of interest is stroke, will be stratified on ischemic or hemorrhagic stroke.

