Unclassified patients	
Binary variable (Yes/No)
 
Equals to "Yes" if Confirmed AF = "No" and Confirmed DVT/PE = "No"
 
The algorithm will be applied on the unclassified patients. Patients with both confirmed AF and DVT/PE will be excluded.
 
Equals to "No" in other cases

Then, a logistic model included 14 independent covariables will be applied on unclassified patients to identify AF outpatients initiating OAC ([Table III](#)).

Table III. Derived variable for the selection of the population – Covariables included in the logistic model

Variable	Definition
Age	
Categorical variable (<65 years old / 65-74 / 75-79 / ≥80 years old)
 
Derived based on the date of birth attributed to the patient after cleaning the data extraction
 
Equals to:
 
 9. "<65 years old" if the absolute difference between the year of index date and the year of birth is strictly lower than 65 years old 10. "65-74" if the absolute difference between the year of index date and the year of birth is between 65 and 74 years old 11. "75-79" if the absolute difference between the year of index date and the year of birth is between 75 and 79 years old 12. "≥80 years old" if the absolute difference between the year of index date and the year of birth is upper than 80 years old 
See also Data Management Plan in section Error! Reference source not found.

Gender	Binary variable (Female / Male) Equals to the value attributed to the patient after cleaning the data extraction See Data Management Plan in section Error! Reference source not found.
Cardiologist prescriber	Binary variable (Yes / No) Equals to "Yes" if the prescriber of the initiation of the OAC is a cardiologist Code CNAM repository (variable PSE_SPE_COD): 03 Equals to "No" in other cases
Initiation of beta-blockers	Binary variable (Yes / No) Equals to "Yes" if the patient has reimbursements for at least one dispensation at pharmacy of any beta-blockers during the 6 weeks preceding the first date of OAC delivery and with no filled prescription for the medication during the previous 180 days ATC codes: C07xxxx Equals to "No" in other cases
Use of beta-blockers	Binary variable (Yes / No) Equals to "Yes" if the patient has reimbursements for at least one dispensation at pharmacy of any beta-blockers during the 6 weeks preceding the first date of OAC delivery ATC codes: C07xxxx Equals to "No" in other cases

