Age ≥ 80 years old	
Binary variable (<80 years old / ≥ 80 years old)
 
Derived based on the date of birth attributed to the patient after cleaning the data extraction
 
Equals to:
 
 13. “<80 years old” if the absolute difference between the year of index date and the year of birth is strictly lower than 80 years old 14. “≥ 80 years old” if the absolute difference between the year of index date and the year of birth is upper than 80 years old 
See also Data Management Plan in section Error! Reference source not found.

History of coronary arterial disease (CAD)	
Binary variable (Yes / No)
 
Equals to “Yes” if the patient meets any criterion below on or in the 2 years prior to the index date:
 
 15. Is hospitalized with any diagnosis (i.e., main, related or associated diagnosis) of coronary arterial disease 
ICD-10 codes: I21.x, I22.x, I24.x, I25.x
 
OR
 
 – Is covered by the LTD status for coronary arterial disease at least one day 
ICD-10 codes: I21.x, I22.x, I24.x, I25.x
 
Equals to “No” in other cases

Claims-based Frailty Index (CFI) (for frail patients’ derivation)	
Continuous variable (between 0 and 1)
 
Claims-based frailty index (CFI) estimates a deficit-accumulation frailty index from a clinical assessment using International Classification of Diseases (ICD) diagnosis codes, Current Procedural Terminology (CPT) codes, and Healthcare Common Procedure Coding System (HCPCS) codes in the prior 2 years in administrative claims data.
 
See more details on calculation of CFI in Appendix 22

Frail patients	
Binary variable (Yes / No)
 
Equals to “Yes” if the Claims based Frailty Index (CFI) is upper or equal to 0.20
 
See Table I variable Claims based Frailty Index (CFI)

Active cancer	Binary variable (Yes / No)

Equals to “Yes” if the patient meets any criterion below in the 2 years before index date:
 
16. Is hospitalized with any discharge diagnosis (i.e., main, related or associated diagnosis) of active cancer
 
ICD-10 codes: C00.x to C80.x, D00.x to D09.x, D37.x to D48.x, Z51.0, Z51.1
 
OR
 
 – Is covered by the LTD status for active cancer at least one day 
ICD-10 codes: C00.x to C80.x, D00.x to D09.x, D37.x to D48.x, Z51.0, Z51.1
 
Equals to “No” in other cases
	

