9.7.3 Planned Analysis for the Primary Objective

9.7.3.1 To estimate the incidence rate of stroke (ischemic or hemorrhagic), major bleeding and death in AF patients exposed to OAC (VKA or DOAC) and unexposed to OAC

The analysis of incidence rate for the first occurrence of each event of interest (stroke, major bleeding and death) will be conducted in the population of AF incident patients excluding those with a reported outcomes of interest up to 30 days prior index date.

As a reminder, incident AF patients will be the patients newly diagnosed AF during the inclusion period i.e., with a date of first diagnosis of AF, identified by the date of the start of LTD or of the index hospital stay during inclusion period, or the date of initiation of the OAC.

Event rates will be estimated over the 4-year period 2016-2019, in the overall population and according to the treatment exposure.

The incidence rate for each event of interest (stroke, major bleeding and death) will be defined as the number of events occurring during the follow-up period divided by the number of person-years of follow-up (sum of durations of follow-up period for incident patients).

Incidence rates in unexposed patients will be standardized by age using exposed patients as the population of reference.

Analyses will be descriptive in nature (proportion and 95% confidence interval).

Event rates will also be displayed by sub-populations (see section [9.2.3.4](#)).

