9.7.4.2 Comparison of the incidence of stroke, major bleeding, death

Analyses will be performed independently for each event of interest stroke, major bleeding and death.

Survival analysis will be performed to compare incidence rate (stroke, major bleeding or death) in AF incident patients exposed and unexposed to OAC therapy **excluding those with a reported outcomes of interest up to 30 days prior index date**, using a Cox regression model. The Cox regressions models will consider the first event of interest occurring in AF incident patients exposed and unexposed to OAC. OAC exposure will be considered as time-dependent variable and the models will be adjusted for covariates defined below. By applying the OAC exposure variable as a time dependent variable, estimates of Hazard Ratio will account for switches and discontinuations. Time-dependent exposure Cox proportional hazards models will be used to estimate:

- The Crude hazard ratio (i.e. the incidence rate ratio), and therefore the risk of each outcome at any point during the follow-up since index date
- The adjusted hazard ratio on potential confounders including patient:
 - Time-fixed confounders: sex, age (<80, 80-90, >90 years old), prescriber's specialty at initiation of OAC, having malnutrition (yes/no), risk of falls (yes/no), morbid obesity (yes/no), history of stroke (yes/no), history of major bleeding (yes/no), at least one visit to a nursing home (yes/no), history of dementia (yes/no), concomitant treatments (e.g. receiving at least one antiplatelet drugs (yes/no), other anticoagulant drugs (yes/no), etc. - cf. *Table XV for all confounders*)
 - Time-dependent confounders: AOC treatment exposure

In a first model, patient exposure will be modelled according to five categories: exposure to apixaban, dabigatran or rivaroxaban, exposure to VKA or unexposed patients. In a second model, exposure to DOACs will be integrated instead of exposure to apixaban, dabigatran or rivaroxaban. For both models, the reference for comparison will be VKA exposure.

Same models will be performed on AF incident patients with a high thromboembolic risk (if modified CHAD₂DS₂VASC score is ≥ 2 for males and ≥ 3 females). Patient exposure will be modelled according to three categories: exposure to DOAC (Apixaban, Dabigatran or Rivaroxaban), exposure to VKA or unexposed patients. The reference for comparison will also be VKA exposure.

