Death	xx.x (xx.x)	xx.x (xx.x)	xx.x (xx.x)
Lost to follow-up	xx.x (xx.x)	xx.x (xx.x)	xx.x (xx.x)
End of study period	xx.x (xx.x)	xx.x (xx.x)	xx.x (xx.x)
Duration of the follow-up in years			
Mean (std)	xx.x (xx.x)	xx.x (xx.x)	xx.x (xx.x)
Median	xx.x	xx.x	xx.x
Q1 - Q3	xx.x - xx.x	xx.x - xx.x	xx.x - xx.x
Min - Max	xx.x - xx.x	xx.x - xx.x	xx.x - xx.x
Duration group of the follow-up in years: n (%)			
[0-1[xx.x (xx.x)	xx.x (xx.x)	xx.x (xx.x)
[1-2[xx.x (xx.x)	xx.x (xx.x)	xx.x (xx.x)
[2-3[xx.x (xx.x)	xx.x (xx.x)	xx.x (xx.x)
[3-4[xx.x (xx.x)	xx.x (xx.x)	xx.x (xx.x)
[4-5]*	xx.x (xx.x)	xx.x (xx.x)	xx.x (xx.x)

*This category will be display only for the sensitivity analysis (up to 2020)

2. Shell Tables and Figures of Results of the Planned Analysis for the Primary Objective

Table A2. Incidence rate for stroke, major bleeding and death in AF incidents patients between 2016 and 2019 in France – <POPULATION>

<POPULATION>	Stroke				Major bleeding				Death			
	n	N	Crude	Standardized **	n	N	Crude	Standardized %**	n	N	Crude	Standardized **
Overall	x	x	x,x [x,x;x,x]	NA	x	x	x,x [x,x;x,x]	NA	x	x	x,x [x,x;x,x]	NA
CI 95%				NA				NA				NA
Unexposed to OAC*	x	x	x,x [x,x;x,x]	x,x [x,x;x,x]	x	x	x,x [x,x;x,x]	x,x [x,x;x,x]	x	x	x,x [x,x;x,x]	x,x [x,x;x,x]
CI 95%												
Exposed to OAC	x	x	x,x [x,x;x,x]	NA	x	x	x,x [x,x;x,x]	NA	x	x	x,x [x,x;x,x]	NA
CI 95%				NA				NA				NA
VKAs	x	x	x,x [x,x;x,x]	NA	x	x	x,x [x,x;x,x]	NA	x	x	x,x [x,x;x,x]	NA
CI 95%				NA				NA				NA
DOACs	x	x	x,x [x,x;x,x]	NA	x	x	x,x [x,x;x,x]	NA	x	x	x,x [x,x;x,x]	NA
CI 95%				NA				NA				NA
Apixaban	x	x	x,x [x,x;x,x]	NA	x	x	x,x [x,x;x,x]	NA	x	x	x,x [x,x;x,x]	NA
CI 95%				NA				NA				NA
Dabigatran	x	x	x,x [x,x;x,x]	NA	x	x	x,x [x,x;x,x]	NA	x	x	x,x [x,x;x,x]	NA
CI 95%				NA				NA				NA
Rivaroxaban	x	x	x,x [x,x;x,x]	NA	x	x	x,x [x,x;x,x]	NA	x	x	x,x [x,x;x,x]	NA
CI 95%				NA				NA				NA

OAC: Oral anticoagulant; DOACs: Direct oral anticoagulants; VKAs: Antivitamins K; NA, not applicable.

n: number of events of interest; N: number of person-years of follow-up

*Unexposed and exposed to OAC correspond to the period of time where the patients are not exposed to OAC and exposed to OAC, respectively

%: Incidence of the event of interest; CI 95%: 95% confidence interval

**: Standardized on age group (<65 years old; 65-74 years old; 75-79 years old; ≥80 years old) using the exposed population as reference

<POPULATION>: Incidence rate of events will be stratified in the following sub-groups:

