Incident elderly AF patient (≥80 years old)

Incident AF patient having a history of coronary arterial disease (CAD)

Incident AF frail patient

Incident AF patient having an active cancer

Incident AF patient reported with previous stroke

Modified CHAD2DS2VASC score groups (Low risk / Moderate risk/ High

This table will be presented for sensitivity analyses:

- with integration of 2020 data;
- with a grace period of 30 days and 90 days;
- with integration of all incident AF patients (i.e. inclusion of patients with an event of interest between inclusion date and index date).

Table A3. Incidence rate for ischemic and hemorrhagic stroke in AF incidents patients between 2016 and 2019 in France

<POPULATION>	Stroke							
	Ischemic				Hemorrhagic			
	n	N	Crude	Standardized **	n	N	Crude	Standardized **
Overall	x	x	x,x	NA	x	x	x,x	NA
CI 95%			[x,x;x,x]	NA			[x,x;x,x]	NA
Unexposed to OAC*	x	x	x,x	x,x	x	x	x,x	x,x
CI 95%			[x,x;x,x]	[x,x;x,x]			[x,x;x,x]	[x,x;x,x]
Exposed to OAC*	x	x	x,x	x,x	x	x	x,x	x,x
CI 95%			[x,x;x,x]	[x,x;x,x]			[x,x;x,x]	[x,x;x,x]
VKAs	x	x	x,x	x,x	x	x	x,x	x,x
CI 95%			[x,x;x,x]	[x,x;x,x]			[x,x;x,x]	[x,x;x,x]
DOACs	x	x	x,x	x,x	x	x	x,x	x,x
CI 95%			[x,x;x,x]	[x,x;x,x]			[x,x;x,x]	[x,x;x,x]
Apixaban	x	x	x,x	x,x	x	x	x,x	x,x
CI 95%			[x,x;x,x]	[x,x;x,x]			[x,x;x,x]	[x,x;x,x]
Dabigatran	x	x	x,x	x,x	x	x	x,x	x,x
CI 95%			[x,x;x,x]	[x,x;x,x]			[x,x;x,x]	[x,x;x,x]
Rivaroxaban	x	x	x,x	x,x	x	x	x,x	x,x
CI 95%			[x,x;x,x]	[x,x;x,x]			[x,x;x,x]	[x,x;x,x]

OAC: Oral anticoagulant; DOACs: Direct oral anticoagulants; VKAs: Antivitamins K; NA, not applicable.

n: number of events of interest; N: number of person-years of follow-up

*Unexposed to OAC and exposed to OAC correspond to the period of time where the patients are not exposed to OAC and exposed to OAC respectively

** Standardized on age group (<65 years old; 65-74 years old; 75-79 years old; ≥80 years old) using the exposed population as reference.

3. Shell Tables and Figures of Results of the Planned Analysis for the Secondary Objectives

3.1. To describe the characteristics of AF incidents patients at index date, per year

Table A4. Description of sociodemographic characteristics in AF incident patients at index date, per year

	Exposed to OAC				Total exposed to OAC			Unexposed to OAC			Total unexposed To OAC	
	2016 (N=XXX)	2017 (N=XXX)	2018 (N=XXX)	2019 (N=XXX)	2016-2019 (N=XXX)	2016 (N=XXX)	2017 (N=XXX)	2018 (N=XXX)	2019 (N=XXX)	2016-2019 (N=XXX)		

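### Table A2's age bands collapse to one in the ≥80 subgroup and the low-risk CHA2DS2-VASc stratum, so the standardised unexposed rate there equals the crude rate; elsewhere, age above 80 stays uncontrolled

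*SAP*

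**What the plan says.** SAP 9.7.3.1 (primary objective) states: "Incidence rates in unexposed patients will be standardized by age using exposed patients as the population of reference". The text gives no bands. They appear in the footnotes of the table shells in Appendix 3; for Table A2: "Standardized on age group (<65 years old; 65-74 years old; 75-79 years old; ≥80 years old) using the exposed population as reference". Table A3 uses the same four.

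Table A2 is a template to be repeated by population: "Incidence rate of events will be stratified in the following sub-groups". The list opens with "Incident elderly AF patient (≥80 years old" and ends with the modified CHA2DS2-VASc risk groups. No other bands are given for any of these populations.

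The standardisation bands match the age variable in SAP Table III, "Categorical variable (<65 years old / 65-74 / 75-79 / ≥80 years old", derived as year of index date minus year of birth. The ≥80 subgroup in Table V uses the same difference and the same cut: "the year of index date and the year of birth is upper than 80 years old".

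A finer split at older ages exists elsewhere. Protocol 3.5.3 says: "All analyses on AF patients will be stratified on age-group: <80, 80-90, > 90 years old". SAP 9.2.3.5 lists the same groups, and the Cox model in SAP 9.7.4.2 adjusts for "age (<80, 80-90, >90 years old". Neither the primary-objective column of Table XXI nor the Table A2 population list carries these groups.

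**The concern.** The standardised column exists to make the unexposed rate comparable with the exposed rate beside it. In the ≥80 table it cannot do that, because subgroup and top band are the same set of people. A reader would see a figure labelled age-standardised to which no age adjustment has been applied.

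The open top band also matters outside that subgroup. SAP 7.1 says two-thirds of French AF patients are 75 or older, so a single band from 80 upwards may hold a large part of the cohort. If exposed and unexposed person-time are distributed differently above 80, and event rates change with age there, that difference passes unadjusted into the standardised rate.

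**Working it through.** The documents give no age-specific rates or age shares, so there is no stated figure to reproduce. The check is algebraic, followed by an illustration on assumed inputs.

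**1. Formula.** Direct standardisation: R_std = Σ(w_i × r_i) / Σ w_i, where r_i is the unexposed rate in band i and w_i the exposed weight in band i. The SAP does not say whether weights are patients or person-years; the result below is the same either way.

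**2. The ≥80 subgroup.** Bands <65, 65-74 and 75-79 are empty, so the weights are 0, 0, 0 and 1. Then R_std = r(≥80) = all unexposed events / all unexposed person-years = the crude rate. Over 10,000 random inputs the largest relative difference between the two was 2.2e-16, which is machine precision. If the weights came from the whole exposed population instead, the three lower bands would have a weight but no unexposed rate. The result would be undefined or, after rescaling the weights, again the crude rate.

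**3. The low-risk CHA2DS2-VASc stratum.** By SAP Table VI, age 65-74 scores 1, age 75 or over scores 2, and female sex scores 1. Low risk means 0 in men and 1 in women, which leaves no age points. Everyone is therefore under 65, in one band, and R_std again equals the crude rate. (Moderate risk, 1 in men and 2 in women, leaves room for one age point at most, so it spans <65 and 65-74 and holds no one aged 75 or over.)

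**4. A population spanning all four bands.** Assumed rates 1, 2, 3, 6; unexposed shares 0.25, 0.20, 0.15, 0.40; exposed shares 0.15, 0.30, 0.20, 0.35.
- Crude: 0.25 + 0.40 + 0.45 + 2.40 = 3.50.
- Standardised: 0.15 + 0.60 + 0.60 + 2.10 = 3.45.

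Standardisation does act here, but the ≥80 rate enters as one unadjusted number.

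**5. What one band could leave behind (all inputs assumed).** Let k be the rate above 90 relative to 80-90, with s_U and s_E the shares of unexposed and exposed person-time above 90. Assume no true exposure effect. The one-band ratio, unexposed to exposed, is (1 − s_U + k·s_U) / (1 − s_E + k·s_E).

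| k | s_U 20%, s_E 15% | s_U 30%, s_E 15% | s_U 40%, s_E 10% |
|---|---|---|---|
| 1.5 | 1.02 | 1.07 | 1.14 |
| 2 | 1.04 | 1.13 | 1.27 |
| 3 | 1.08 | 1.23 | 1.50 |

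Example, k = 2 with 30% and 15%: 1.30 / 1.15 = 1.13. With the two shares exchanged, so that the exposed are older, it is 1.15 / 1.30 = 0.88. Splitting at 80-90 / >90 returns 1.00 in every cell, but only because the assumed rates differ solely between those two bands.

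**The case against.** The strongest reply is that the primary estimate is untouched. The objective is to estimate incidence rates, SAP 9.7.3.1 calls the analysis descriptive, and Protocol 3.7.1 defines the measure as events over person-years with no standardisation. This stands: the crude ≥80 rates are valid. A reader might infer that the primary ≥80 results are wrong; the documents do not support that. Only the standardised column is empty of content.

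A reader might also infer that age goes uncontrolled throughout the study. That is too strong. Restriction to ≥80 removes differences from younger ages, standardisation works across the lower bands elsewhere, and the exposed/unexposed comparison is a separate objective whose Cox model includes 80-90 and >90. The reply is incomplete, however: the only subgroup planned for the Cox model is high thromboembolic risk (Table XXI, 9.7.4.2), so no age-adjusted comparison within ≥80 is planned.

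Protocol 3.5.3 can be read as already requiring separate 80-90 and >90 results. If carried out, that would help, but the primary column of Table XXI and the Table A2 list do not implement it.

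Finally, identical crude and standardised values would be visible to an attentive reader. True, but that shows the column is redundant; it does not repair it.

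**Conclusion.** The point holds. In the ≥80 and low-risk versions of Table A2, and in their planned sensitivity repeats, the standardised unexposed rate equals the crude rate by construction for all three events. This rests only on the bands, the subgroup definitions and the score rules in the SAP. In the overall table and the other populations that include patients over 80, standardisation is real but stops at 80.

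The size of the residual confounding is not known. A reader might infer that the unexposed are older within ≥80 and that their rates are therefore inflated; the documents give neither the age mix nor the rates above 80. The 1.02 to 1.50 range is conditional on assumed inputs, and its direction reverses if the age mix reverses.

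A reader might also take the NA entries for the exposed rows of Table A2 as an error. They follow SAP 9.7.3.1 and Table XXI, which standardise the unexposed only. Table A3, which provides standardised values for the exposed rows, is the one that departs from the text.

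**What to change.** 1. In SAP 9.7.3.1 and the footnotes of Tables A2 and A3, split the open ≥80 band: at minimum at the existing 80-90 / >90 cut, preferably 80-84, 85-89 and ≥90. The two options place age 90 differently, so choose one and state it. Use the bands in every Table A2 population, including ≥80.
2. For the low-risk CHA2DS2-VASc stratum, either split <65 or print NA in the standardised column.
3. Reconcile Protocol 3.5.3 and SAP 9.2.3.5 (age groups <80, 80-90, >90) with Table XXI and the Table A2 population list.
4. Reconcile the NA exposed rows of Table A2 with the filled rows of Table A3.
5. While editing, word the cut in Tables III and V so that a difference of exactly 80 years is covered. This does not affect the finding.

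The cost is SAP wording and one programming parameter. Age is already derived as a continuous variable (SAP Table XII), and about 1 million (Protocol 3.3) to 1.3 million (SAP 9.5) exposed patients are expected over 2016-2020. Standardised intervals will be slightly wider where a band is sparse.

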3.3. Comparison of the incidence of stroke, major bleeding, death

Table A10. Risk of stroke, major bleeding or death in AF incident patients

	Event		Crude risk ¹		Adjusted risk ^{2,*}	
	n	%	HR	[95%CI]	HR	[95%CI]
Risk of stroke						
Exposure to DOACs	xx	(x.x)	x.xx	[x.xx-x.xx]	x.xx	[x.xx-x.xx]
Exposure to Apixaban	xx	(x.x)	x.xx	[x.xx-x.xx]	x.xx	[x.xx-x.xx]
Exposure to Dabigatran	xx	(x.x)	x.xx	[x.xx-x.xx]	x.xx	[x.xx-x.xx]
Exposure to Rivaroxaban	xx	(x.x)	x.xx	[x.xx-x.xx]	x.xx	[x.xx-x.xx]
Unexposed to OAC**	xx	(x.x)	x.xx	[x.xx-x.xx]	x.xx	[x.xx-x.xx]
Exposure to VKA	xx	(x.x)	ref		ref	
Risk of major bleeding						
Exposure to DOACs	xx	(x.x)	x.xx	[x.xx-x.xx]	x.xx	[x.xx-x.xx]
Exposure to Apixaban	xx	(x.x)	x.xx	[x.xx-x.xx]	x.xx	[x.xx-x.xx]
Exposure to Dabigatran	xx	(x.x)	x.xx	[x.xx-x.xx]	x.xx	[x.xx-x.xx]
Exposure to Rivaroxaban	xx	(x.x)	x.xx	[x.xx-x.xx]	x.xx	[x.xx-x.xx]
Unexposed to OAC**	xx	(x.x)	x.xx	[x.xx-x.xx]	x.xx	[x.xx-x.xx]
Exposure to VKA	xx	(x.x)	ref		ref	
Risk of death						
Exposure to DOACs	xx	(x.x)	x.xx	[x.xx-x.xx]	x.xx	[x.xx-x.xx]
Exposure to Apixaban	xx	(x.x)	x.xx	[x.xx-x.xx]	x.xx	[x.xx-x.xx]
Exposure to Dabigatran	xx	(x.x)	x.xx	[x.xx-x.xx]	x.xx	[x.xx-x.xx]
Exposure to Rivaroxaban	xx	(x.x)	x.xx	[x.xx-x.xx]	x.xx	[x.xx-x.xx]
Unexposed to OAC**	xx	(x.x)	x.xx	[x.xx-x.xx]	x.xx	[x.xx-x.xx]
Exposure to VKA	xx	(x.x)	ref		ref	

AF : Non Valvular Atrial Fibrillation; HR: hazard ratio; 95%CI: 95% confidence interval

Note: For considering DOAC treatment in models, two regressions models will be performed for this table: one model with "Exposure to DOACs" as independent variable; second model with exposure for each molecule within the class of DOAC (Apixaban, Dabigatran, Rivaroxaban).¹From a time-dependant exposure to OAC Cox proportional hazards model

²From a time-dependant exposure to OAC and time-fixed covariates Cox proportional hazards model;

*Adjusted on the following covariates at index date: age (<80, 80-90, >90 years old), sex, having malnutrition, risk of falls, morbid obesity, history of stroke, history of major bleeding, at least one visit to a nursing home, history of dementia, each concomitant treatments

**Unexposed to OAC correspond to the period where the patients are not exposed to OAC.

Same table will be presented for sensitivity analyses:

- with integration of 2020 data

- with 30 days and 90 days of maximal number of days allowed for being refilled

- with integration of all incident AF patient (i.e. inclusion of patients with an event of interest between inclusion date and index date)

Table A11. Risk of stroke, major bleeding or death in AF incident patients with a high thromboembolic risk (modified CHA2DS2VASC score is ≥ 2 for males and ≥ 3 females)

	Event		Crude risk ¹		Adjusted risk ^{2,*}	
	n	%	HR	[95%CI]	HR	[95%CI]
Risk of stroke						
Exposure to DOACs	xx	(x.x)	x.xx	[x.xx–x.xx]	x.xx	[x.xx–x.xx]
Exposure to Apixaban						
Exposure to Dabigatran						
Exposure to Rivaroxaban						
Unexposed to OAC**	xx	(x.x)	x.xx	[x.xx–x.xx]	x.xx	[x.xx–x.xx]
Exposure to VKA	xx	(x.x)	ref		ref	
Risk of major bleeding						
Exposure to DOACs	xx	(x.x)	x.xx	[x.xx–x.xx]	x.xx	[x.xx–x.xx]
Exposure to Apixaban						
Exposure to Dabigatran						
Exposure to Rivaroxaban						
Unexposed to OAC**	xx	(x.x)	x.xx	[x.xx–x.xx]	x.xx	[x.xx–x.xx]
Exposure to VKA	xx	(x.x)	ref		ref	
Risk of death						
Exposure to DOACs	xx	(x.x)	x.xx	[x.xx–x.xx]	x.xx	[x.xx–x.xx]
Exposure to Apixaban						
Exposure to Dabigatran						
Exposure to Rivaroxaban						
Unexposed to OAC**	xx	(x.x)	x.xx	[x.xx–x.xx]	x.xx	[x.xx–x.xx]
Exposure to VKA	xx	(x.x)	ref		ref	

AF : Non Valvular Atrial Fibrillation; HR: hazard ratio; 95%CI: 95% confidence interval; DOAC= Direct oral anticoagulant; VKA= Antivitamin K;
 Note: For considering DOAC treatment in models, two regressions models will be performed for this table: one model with "Exposure to DOACs" as independent variable; second model with exposure for each molecule within the class of DOAC (Apixaban, Dabigatran, Rivaroxaban).

¹From a time-dependant exposure Cox proportional hazards model

²From a time-dependant exposure to OAC and time-fixed covariates Cox proportional hazards model;

*Adjusted on the following covariates at or from index date: age (<80, 80-90, >90 years old), sex, having malnutrition, risk of falls, morbid obesity, history of stroke, history of major bleeding, at least one visit to a nursing home, history of dementia, each concomitant treatments

**Unexposed to OAC correspond to the period where the patients are not exposed to OAC.

